## 6. ANALYSES AND SUMMARIES

### 6.1. Primary Endpoint(s)

#### 6.1.1. Percentage Change from Baseline in EASI Score at Week 6 & Change from Baseline PASI Score at Week 6

##### 6.1.1.1. Main Analysis

- Estimand strategy: Primary Estimand ([Section 2.1.1](#)). This estimand is intended to provide an estimate of the treatment effect in the absence of prohibited medication use in a population that may or may not be fully compliant with the treatment.
- Analysis set: mITT ([Section 4](#)) using data prepared in the description of the full analysis set.
- Analysis methodology: Percent change from baseline will be analyzed using an ANCOVA with the observed (or imputed) Week 6 change from baseline EASI score as the dependent variable with treatment arm and baseline EASI score as the independent variables. Same method will be used for change from baseline PASI score at Week 6.
- Intercurrent events and missing data: Data prohibited medication will be excluded and set to missing. Missing data which will be multiply imputed using a control-based strategy as described in ([Section 5.3](#)). A thousand (1000) imputed datasets will be used in the analysis and results combined using PROC MIANALYZE.
- The least-squares (LS) means, the 90% confidence interval for the LS means, the difference between the LS means for each pair of treatment groups, and the corresponding 90% confidence interval will be presented.

##### 6.1.1.2. Sensitivity/Supplementary Analyses

###### Sensitivity Analyses:

- To assess the impact of baseline distribution, the main analysis will be repeated with the ANCOVA model replaced by an ANOVA model (excluding baseline as a covariate).

###### Supplementary Analyses:

- Mixed model repeated measures (MMRM) models will be used (assuming missing data are missing at random). The fixed effects of treatment, visit, and treatment by visit interaction will be included. Visit will be modeled as a categorical covariate.

## 6.2. Secondary Endpoint(s)

### 6.2.1. IGA/PGA Responses at Week 6

#### 6.2.1.1. Main Analysis

- Estimand strategy: Secondary estimand ([Section 2.1.2](#)) use a composite endpoint strategy. This estimand is intended to provide an estimate of the treatment effect in the absence of prohibited medication use in a population that may or may not be fully compliant with the treatment.
- Analysis set: mITT ([Section 4](#)) using data prepared in the description of the Secondary Estimand Categorical Endpoint Set.
- Analysis methodology: Risk differences will be analyzed using the method of Chan and Zhang (1999). Confidence Interval of binomial proportion will be reported using Blyth-Still-Casella method.
- Intercurrent events and missing data: These have been accounted for in the preparation of the Secondary Estimand Categorical Endpoint Set ([Section 5.3](#)). This prepared data set has no missing values.
- Proportions, risk differences and 90% confidence intervals will be presented.

#### 6.2.2. Other Binary Secondary Endpoints

EASI 75, PP-NRS response Rate, IGA of clear or almost clear, PASI 75, PGA of clear or almost clear and PSI response rate will be analyzed the same way as described in [Section 6.2.1](#).

#### 6.2.3. Other Continuous Secondary Endpoints

Change from baseline EASI, Percent change from baseline in affected BSA (in AD patients), Change from baseline PASI (except Week 6), Percent change from baseline PASI, Percent change from baseline in affected BSA (in Psoriasis patients)

##### 6.2.3.1. Main Analysis

- Estimand strategy: Primary Estimand ([Section 2.1.1](#)). This estimand is intended to provide an estimate of the treatment effect in the absence of prohibited medication use in a population that may or may not be fully compliant with the treatment.

- Analysis set: mITT ([Section 4](#)) using data prepared in the description of the Primary Estimand Continuous Endpoint Set.
- Analysis methodology: Percent and absolute change from baseline at week 6 will be analyzed using an ANCOVA with the observed endpoint data as the dependent variable with treatment arm and baseline endpoint value as the independent variables.
- Intercurrent events and missing data: Data prohibited medication will be excluded and set to missing. For ANCOVA analysis at week 6, missing data which will be multiply imputed using a control-based strategy as described in ([Section 5.3](#)). A thousand (1000) imputed datasets will be used in the analysis and results combined using PROC MIANALYZE.
- The least-squares (LS) means, the 90% confidence interval for the LS means, the difference between the LS means for each pair of treatment groups, and the corresponding 90% confidence interval will be presented.

CCI

CCI

## **6.5. Subset Analyses**

There are no subset analyses are planned.

## **6.6. Baseline and Other Summaries and Analyses**

### **6.6.1. Baseline Summaries**

Demographic and baseline characteristics will be summarized by randomized treatment group for all randomized and treated subjects. Continuous variables will be summarized using mean and standard deviation. Categorical variables will be summarized using relative frequency. Key demographic and baseline variables to be summarized include: geographic region, age, gender, race, ethnicity, height, weight, body mass index, disease duration, baseline EASI score, baseline IGA, baseline PASI score, baseline PGA, baseline BSA score etc.

### **6.6.2. Study Conduct and Participant Disposition**

Subjects' evaluation, disposition and discontinuation will be summarized according to CaPS.

### **6.6.3. Study Treatment Exposure**

A summary of dosing compliance by treatment group will be provided.

The exposure to study drug will be summarized by the total number of days of dosing, mean/median number of days of exposure and number and percent of subjects in exposure duration categories.

### **6.6.4. Concomitant Medications and Nondrug Treatments**

Prior drug and non-drug treatment, concomitant drug and non-drug treatment will be summarized according to CaPS.

## 6.7. Safety Summaries and Analyses

The analysis population for safety is described in [Section 4](#). Safety and tolerability will be assessed by clinical review of all relevant parameters including adverse experiences (AEs) and laboratory tests. A complete list of laboratory parameters can be obtained in [Section 8.2.5](#) of the protocol.

All the tables, listings and graphs for adverse events, lab parameters and vital sign and ECG will follow Pfizer standards. The binary safety endpoints including the incidences of on-treatment AEs, withdrawals due to AEs and serious AEs will be analyzed using the exact test described in [Section 5.2.1](#).

### 6.7.1. Adverse Events

All the tables, listings and graphs for adverse events, lab parameters and vital sign and ECG will follow Pfizer standards. The binary safety endpoints including the incidences of on-treatment AEs, withdrawals due to AEs and serious AEs will be analyzed using the exact test described in [Section 5.2.1](#).

There will be no adjustment for multiple comparisons or stratification factors in the analyses unless specified. AEs will be arranged in the output sorted in descending point estimate of the risk difference within system organ class. Footnotes in the outputs will include the methods used to derive any p-values and confidence intervals as per Pfizer standards.

It should be recognized that most studies are not designed to reliably demonstrate a causal relationship between the use of a pharmaceutical product and an adverse event or a group of adverse events. Except for select events in unique situations, studies do not employ formal adjudication procedures for the purpose of event classification. As such, safety analysis is generally considered as an exploratory analysis and its purpose is to generate hypotheses for further investigation.

### 6.7.2. Laboratory Data

Laboratory data will be listed and summarized in accordance with the CaPS reporting standards. Summaries of subjects meeting pre-specified monitoring and discontinuation criteria will be created using methods for categorical data.

### 6.7.3. Vital Signs

Vital signs will be summarized at baseline, Weeks 2, 4, and 6/End of Treatment visits.

#### **6.7.4. Electrocardiograms**

Categorical summary tables will be summarized by treatment and time post-dose using sponsor reporting standards. Baseline is as defined in [Section 3.5.4](#). A listing of ECG comments on findings and normal/abnormal results will be provided.

#### **6.7.5. Physical Examination**

Physical examinations will be summarized at baseline and all-available post-baseline visits.

### **7. INTERIM ANALYSES**

No interim analyses are planned.

## 9. APPENDICES

### Appendix 1. Summary of Efficacy Analyses

| Efficacy Endpoint  | Analysis Type | Population | Data Inclusion and Rules for Handling Intercurrent Events and Missing Data | Analysis Model |
|---|----------------------|-------------------|---|-----------------------|
| Week 6 PCFBL in EASI / CFBL in PASI   | Primary Analysis     | FAS               | MI  | ANCOVA                |
| PCFBL in EASI / CFBL in PASI  | Sensitivity Analysis | FAS               | OC  | MMRM                  |
| Week 6 IGA / PGA Response   | Secondary Analysis   | FAS               | NRI   | Chan & Zhang          |
| Week 6 CFBL in EASI / PCFBL in PASI / PCFBL in BSA  | Secondary Analysis   | FAS               | MI  | ANCOVA                |
| EASI 75 / PP-NRS Rate / IGA of clear or almost clear / PASI 75 / PGA of clear or almost clear | Secondary Analysis   | FAS               | NRI   | Chan & Zhang          |

CCI

PCFBL= Percent change from baseline; CFBL= Change from baseline; ANCOVA = Analysis of Covariance; NRI = Non Responder Imputation; OC = Observed Cases.

## Appendix 2. Data Derivation Details

### Appendix 2.1. Definition and Use of Visit Windows in Reporting

Visit windows will be used for efficacy variables, and for any safety data that display or summarize by study visit. For other endpoints (e.g., ECG, vital signs), visit windows will be applied for summary statistics by study visits if required.

| Visit No.   | Visit Label | Target Day | Visit Window                  |
|---|-------------|------------|-------------------------------|
|   | Screening   | N/A        | $-42 \leq \text{day} \leq -1$ |
| 1   | Baseline*   | 1          | $\text{day} = 1$              |
| 2   | Week 1      | 8          | $2 \leq \text{day} \leq 11$   |
| 3   | Week 2      | 15         | $12 \leq \text{day} \leq 18$  |
| 4   | Week 3      | 22         | $19 \leq \text{day} \leq 25$  |
| 5   | Week 4      | 29         | $26 \leq \text{day} \leq 36$  |
| 6   | Week 6      | 43         | $37 \leq \text{day} \leq 57$  |
| 7   | FUP/EOS     | N/A        | $\text{day} \geq 58$          |
| * Baseline analysis visit window may be considered as $\text{day} \leq 1$ in some analyses (eg, those involving change from baseline). That is, in case that Day 1 observation is missing, the last observation before the first dosing date may be considered as the baseline. The baseline measurements for demography, height, pre-study medical history and medications will be collected at the “Screening” visit. |             |            |                               |

If two or more visits fall into the same window, keep the one closest to the Target Day. If two visits are equally distant from the Target Day in absolute value, the later visit should be used.

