1.3.1. Atopic Dermatitis

ATOPIC DERMATITIS								
Visit Identifier ^a	Screening & Washout	Day 1 (Baseline)	Week 1	Week 2	Week 4	Week 6 (EOT)	Follow-up (EOS)	Early Termination (ET)
Visit Window	Day-42 to -1	N/A	Day 8 ±2	Day 15 ±2	Day 29 ±2	Day 43 ±2	28–35 Days post-last Dose	N/A
Visit Number	1	2	3	4	5	6	7	N/A
Enrollment Procedures								
Informed Consent	X							
Register Subject Using IRT System	X							
Medical History	X	X						
Concomitant/Prior Treatments	X	X	X	X	X	X	X	X
Demography	X							
Eligibility Assessment	X	X						
Randomization		X						
Clinical Assessments								
Complete Physical Examination ^b	X	X				X		
Targeted Physical Examination ^b			X	X	X		X	X
Weight	X	X						
Height	X							
Vital Signs ^c	X	X		X	X	X		X
ECG ^d	X	X				X		
C-SSRS ^e	X							
Laboratory Assessments								
Serum FSH (WONCBP only) or Serum Pregnancy Test (WOCBP only) ^f	X							

ATOPIC DERMATITIS

Visit Identifier ^a	Screening & Washout	Day 1 (Baseline)	Week 1	Week 2	Week 4	Week 6 (EOT)	Follow-up (EOS)	Early Termination (ET)
Visit Window	Day-42 to -1	N/A	Day 8 ±2	Day 15 ±2	Day 29 ±2	Day 43 ±2	28-35 Days post-last Dose	N/A
Visit Number	1	2	3	4	5	6	7	N/A
Urine Pregnancy Test (conducted at study site) ^g		X	X	X	X	X	X	X
Hematology, Chemistry and Urinalysis ^h	X	X	X	X	X	X	X	X
Fibrinogen, hsCRP ^h	X	X	X	X	X	X	X	X

IP Related Processes								
Dispense dosing diary/PROs and instruct on usage	X							
Assess BSA & calculate IP need	X	X	X	X	X			
Body Map		X	X	X	X	X		
Weigh and dispense IP		X	X	X	X			
IP application and observation (at site/at home in case of Home Health Visits)		X	X	X	X	X		
Record dose and time of IP application in dosing diary		X	→	→	→	X		
Collect and weigh returned IP tubes for compliance check			X	X	X	X		X
Review of dosing diary/PROs		X	X	X	X	X	X	X
Collect dosing diary/PROs		X ^k					X	X
AD-Related Clinical Assessments								
EASI	X	X	X	X	X	X	X	X
IGA	X	X	X	X	X	X	X	X

ATOPIC DERMATITIS

Visit Identifier ^a	Screening & Washout	Day 1 (Baseline)	Week 1	Week 2	Week 4	Week 6 (EOT)	Follow-up (EOS)	Early Termination (ET)
Visit Window	Day-42 to -1	N/A	Day 8 ±2	Day 15 ±2	Day 29 ±2	Day 43 ±2	28–35 Days post-last Dose	N/A
Visit Number	1	2	3	4	5	6	7	N/A
BSA	X	X	X	X	X	X	X	X
Safety Monitoring								
Contraception check	X	X	X	X	X	X	X	X
Local Tolerability Assessments ^l		X	X	X	X	X	X	X
Serious and non-serious AE monitoring	X	→	→	→	→	→	X	X
Patient Reported Outcomes (PRO)								
In-clinic completion								
At-home completion								
PP-NRS ^m	X	→	→	X	X	X	X	X

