Two negative pregnancy tests are required before randomization (1 negative serum pregnancy test at screening and 1 negative urine pregnancy test at Day 1 visit). If urine pregnancy test is positive after study intervention application, serum pregnancy test will be conducted, study intervention application paused and sponsor clinician and sponsor medical monitor notified immediately.

Local Tolerability

If a participant experiences severity Grade 3 (severe) or 4 (very severe) on the local tolerability assessment ([Section 8.2.7](#)), study treatment will be discontinued permanently, and participant will proceed to ET visit and follow-up as described in [SoA](#).

If a participant experiences application site reaction of Grade 2 (moderate) on the local tolerability assessment, investigator may temporarily discontinue application of IP for up to 48 hours without consulting the Sponsor. If in the clinical judgment of the investigator IP interruption beyond 48 hours is advisable, the investigator must obtain agreement from the Pfizer medical monitor to continue withholding IP. If temporary IP interruption for more than 5 consecutive days is needed, then the participant should be permanently withdrawn from treatment and should follow-up with the site until complete or near complete resolution of the AE. This dosing gap may occur only once for the same participant.

AEs

Hypersensitivity Reactions: If signs and symptoms of hypersensitivity are attributable to the investigational product, including contact urticaria, it must be discontinued immediately, and appropriate therapy initiated.

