| 
 
To compare the efficacy of PF-07038124 versus vehicle, on measures of disease and symptom severity in participants with mild or moderate AD.
 
 | 
 
Change from baseline in EASI total score at study visit time points specified in the SoA.
 
Proportion of participants achieving IGA score of clear (0) or almost clear (1) at study visit time points specified in the SoA.
 
Percent change from baseline in affected Body Surface Area (BSA) at study visit time points specified in the SoA.
 
 | 
 
All continuous secondary endpoints will be analyzed descriptively and using estimand E1 described above, when appropriate.
 
All categorical secondary endpoints will be analyzed descriptively and using estimand E2 described above, when appropriate.
 
 |
| 
 
To characterize the safety and tolerability of PF-07038124 versus vehicle in participants with mild or moderate AD.
 
                          | 
 
Incidence of treatment emergent adverse events (AEs) and serious adverse events (SAEs), clinically significant changes in vital signs, electrocardiogram (ECG), and laboratory tests.
 
Incidence of severity grades in skin tolerability at times indicated in SoA.
 
   | 
 
There is no defined estimand for these endpoints and they will be analyzed using Pfizer data standards as applicable.
 
  |

CCI

CCI

| PSORIASIS  |  |   |
|---|--|---|
| Objectives   | Endpoints   | Estimands  |
| Primary:   | Primary:  | Primary:   |

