### **3.2. Secondary Endpoint(s)**

#### **For AD:**

- *Proportion of participants achieving IGA score of clear (0) or almost clear (1) (on a 5-point scale) and a reduction from baseline of  $\geq 2$  points at Week 6 and other study visit time points specified in the SoA.*
- *Proportion of participants achieving EASI 75 (75% improvement from baseline) at study visit time points specified in the SoA.*
- *Proportion of participants having  $\geq 4$  points of reduction in weekly averages of Peak Pruritus Numerical Rating Scale (PP-NRS) from baseline at study visit time points specified in the SoA.*
- *Change from baseline in EASI total score at study visit time points specified in the SoA.*
- *Proportion of participants achieving IGA score of clear (0) or almost clear (1) at study visit time points specified in the SoA.*
- *Percent change from baseline in affected Body Surface Area (BSA) at study visit time points specified in the SoA.*
- *Incidence of treatment emergent adverse events (AEs) and serious adverse events (SAEs), clinically significant changes in vital signs, electrocardiogram (ECG), and laboratory tests.*
- *Incidence of severity grades in skin tolerability at times indicated in SoA.*

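### The SAP's nearest-to-target window rule can drop the local tolerability grade that stopped treatment, and no visible summary of graded tolerability recovers it

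*SAP*

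**What the plan says.** SAP 3.2 lists, for each indication, the endpoint "Incidence of severity grades in skin tolerability at times indicated in SoA". The schedules of activities in Protocol 1.3.1 and 1.3.2 mark "Local Tolerability Assessments" at Day 1, Weeks 1, 2, 4 and 6, Follow-up and ET, before and just after dosing.

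Protocol 7.1 ties the grade to treatment. "If a participant experiences severity Grade 3 (severe) or 4 (very severe) on the local tolerability assessment", then "study treatment will be discontinued permanently, and participant will proceed to ET visit and follow-up as described in" the schedule of activities.

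For the analysis, SAP 2.1 says: "There is no defined estimand for these endpoints and they will be analyzed using Pfizer data standards as applicable". SAP 6.7 covers adverse events, laboratory data, vital signs, ECG and physical examination, and its visible text has no table of tolerability grades.

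SAP Appendix 2.1 sets the scope of windowing: "Visit windows will be used for efficacy variables, and for any safety data that display or summarize by study visit". Within a window the instruction is "If two or more visits fall into the same window, keep the one closest to the Target Day", and for ties "If two visits are equally distant from the Target Day in absolute value, the later visit should be used". Its table has rows for Baseline, Weeks 1, 2, 3, 4 and 6 and follow-up, and none for ET.

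**The concern.** Choosing the record nearest the target day is a reasonable way to line up efficacy scores. It suits a graded safety measure poorly, because the record that matters most is the worst one, and that record may come from a visit that was not planned. When such a visit shares a window with a scheduled one, the rule ignores severity. Even a tie is settled by date.

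This is the first study of the ointment in patients with either disease. Protocol 2.2.3 reports local skin reactions in minipigs and a sensitization signal in mice. The grade table is where a reader would look for the severity of local reactions, and the rule can make that table milder than the data collected.

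**Working it through.** **Inputs.**
- Windows and targets (SAP Appendix 2.1): Week 1, Days 2-11, target 8; Week 2, Days 12-18, target 15; Week 3, Days 19-25, target 22; Week 4, Days 26-36, target 29; Week 6, Days 37-57, target 43; follow-up from Day 58.
- Scheduled visits (Protocol 1.3.1 and 1.3.2): Days 8, 15, 29 and 43, each ±2 days. There is no Week 3 visit.
- Follow-up visit: 28 to 35 days after the last dose.
- Arm sizes (Protocol 1.1): 21/(1 − 0.25) = 28 in atopic dermatitis and 12/(1 − 0.25) = 16 in psoriasis, as stated.

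The plan gives no tolerability rate, so there is no planned figure to reproduce.

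**Step 1. ET or unscheduled grade after a scheduled visit.** Place one such record on each of Days 2 to 42 (41 days), after the scheduled visits already held. Keep the record with the smallest |day − target|, and the later one on a tie. With scheduled visits on target:

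| Fate of the record | Days | Count |
|---|---|---|
| Dropped for the earlier scheduled record | 9-11, 16-18, 30-36 | 3 + 3 + 7 = 13 |
| Kept, but labelled Week 3 | 19-25 | 7 |
| Kept under a scheduled visit label | all others | 41 − 13 − 7 = 21 |

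The last row includes Days 8, 15 and 29, where the grade is the scheduled record itself.

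Example: Grade 1 on Day 8 and Grade 3 on Day 10. The distances are |8 − 8| = 0 and |10 − 8| = 2, so Week 1 shows Grade 1.

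**Step 2. Vary the visit days.** Over the 125 combinations of −2 to +2 days for the Week 1, 2 and 4 visits (5 × 5 × 5), between 7 and 13 days are dropped and between 21 and 27 are kept under a scheduled label. The Week 3 count stays at 7. The minimum of 7 occurs with visits on Days 6, 13 and 27. Only Day 11, Day 18 and Days 32-36 are then dropped (1 + 1 + 5).

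**Step 3. The reverse case.** Suppose the Grade 3 or 4 is found at a scheduled visit held early and a milder grade is recorded at ET. With the visit on Day 13 (distance 2), an ET on Days 14 to 17 has distance 1, 0, 1 or 2. It is nearer or tied, so the ET record is kept and the severe grade goes. The same happens with a visit on Day 27 and ET on Days 28 to 31.

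**Step 4. Follow-up after early stopping.** For last dose on Day L, follow-up falls on Days L + 28 to L + 35. It lies wholly in the Week 6 window when L + 28 ≥ 37 and L + 35 ≤ 57, that is, for L from 9 to 22.

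| Last dose | Window that receives the follow-up record |
|---|---|
| Day 1 | Week 4 |
| Days 2-8 | Week 4 or Week 6 |
| Days 9-22 | Week 6 |
| Days 23-29 | Week 6 or follow-up |
| Day 30 onward | Follow-up |

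A grade taken about a month off the ointment, possibly resolved, is then tabulated as an on-treatment visit.

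**Step 5. Scale.** One displaced participant is 1/28 = 3.6% of an atopic dermatitis arm or 1/16 = 6.3% of a psoriasis arm. The number of such participants is an assumption.

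**The case against.** The case against has four parts.

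- **The reactions are captured elsewhere.** Protocol 8.2.7 requires application-site AEs to be recorded with their severity. SAP 6.7.1 analyses AE incidence and withdrawals due to AEs without visit windows. This stands: the reactions should still reach the safety report. It does not restore the grade distribution. AE intensity has three levels (Protocol 10.3.3), while the tolerability scale also has a Grade 4, very severe.
- **The grade that stops treatment may be the scheduled record.** The assessment is done at scheduled visits, and the participant then proceeds to ET. This also stands. Such a record lies within 2 days of target and is lost only in the situation of Step 3.
- **The analysis is deferred to sponsor standards that are not supplied, and part of Protocol 8.2.7 is redacted.** An ET column may exist there, since ET is a scheduled tolerability time. The SAP does not provide one, however, and its written rule covers any safety data shown by visit.
- **The endpoint is defined by visit.** This is right, and a worst-grade summary should be added beside it without replacing it.

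A reader might go further and infer that stopping grades are usually lost, or that later tables show only people who tolerated the ointment. The documents support neither. Displacement needs two records in one window, and an ET record alone in its window is kept. A participant whose last dose is on Day 10 has follow-up on Days 38 to 45, inside the Week 6 window, and so reappears in that table off treatment.

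**Conclusion.** The point holds for the graded tolerability endpoint. As written, Appendix 2.1 can remove the grade that ended treatment on 13 of 41 possible days with visits on target (7 to 13 of 41 over the ±2-day visit windows). It puts a further 7 days under a visit that the schedule does not contain, and it can replace a severe scheduled grade with a milder ET one. It also moves off-treatment follow-up into Week 4 or Week 6. When the displaced grade is the worse one, or the follow-up grade has resolved, the tables look milder than the data.

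These are counts of days, not probabilities: the documents do not say when reactions occur or how many to expect. The conclusion assumes that the rule is applied literally and that no unseen sponsor standard overrides it. It does not extend to the AE and AE-withdrawal analyses, which do not use the windows, or to efficacy.

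**What to change.** In SAP Appendix 2.1, state that nearest-to-target selection does not apply to local tolerability. For the by-visit tables:

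- use the worst grade within each window;
- say how ET is handled, either as its own column or as part of the window;
- say where records on Days 19-25 go, since there is no Week 3 visit;
- keep post-treatment follow-up out of the on-treatment windows.

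Beside the by-visit endpoint, add one table of the worst post-baseline grade per participant, by arm and indication, on the Safety Analysis Set. It should use all scheduled, unscheduled and ET records. A stopping grade then counts on whichever of the 41 days it was recorded.

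The cost is SAP wording and one table. It needs no new data and no change to any stopping rule.
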